Symptom burden in cancer survivors. Physical and psychological symptoms are aggravated while cancer survivors are in treatment.^{103,104} Survivors' symptom burden¹⁰⁵⁻¹¹² is often the primary reason for altering or stopping chemotherapy^{113,114} leading to suboptimal treatment at the very least,¹¹⁵⁻¹¹⁷ and life threatening recurrence or metastasis at the extreme.^{118,119} The prevalence of specific symptoms (e.g., fatigue, pain, depression, anxiety, disturbed sleep, nausea and vomiting, neuropathy)¹²⁰⁻¹²⁵ varies by cancer diagnosis, treatment type, gender, ethnicity and age,^{98,99} variables that will be empirically tested as potential tailoring factors in decision rules that will be formulated in this research. The number of symptoms reported by cancer survivors can be as high as 14.^{126,127} Approximately 30% of cancer survivors report psychological distress (depression and anxiety). Major depression occurs in approximately 16%, and subthreshold depressive disorders occur in 22% of cancer survivors during treatment.²⁸ These prevalence rates are about 3 times higher than in the general population. Even when depression and anxiety do not meet threshold for clinical diagnoses, these symptoms are still associated with significant health impairments, yet are highly treatable,^{128,129} and will be in this trial, potentially saving healthcare costs and improving outcomes. Further, in our past studies, Latinas with breast cancer reported a higher number and more symptom burden/distress than did non-Hispanic white women with similar diagnoses.³¹ Therefore, we will enroll an ethnically diverse sample (includes 30% Hispanic/Latino participants) in this trial to address a significant symptom management need. Given the increasing population of Hispanic cancer survivors, providing and testing an intervention in the participant's primary language could have national significance. A series of longitudinal studies¹³⁰⁻¹³³ including those conducted by this team^{130,131}, found an association between increasing symptom prevalence and poorer physical and emotional functioning. Our team's past work¹³⁴ and that of others¹³⁵ documented the associations between reductions in symptoms and lower number of hospitalizations, office and ED visits.¹⁰ The proposed interventions are significant because they will address the multiple symptoms experienced by survivors during treatment and the associated health care service use.

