3.0 SAMPLE ELIGIBILITY CRITERIA

Specific inclusion/exclusion requirements which must be met for entry.

Inclusion criteria for the survivors are: **1)** age 18 or older; **2)** undergoing chemotherapy, hormonal therapy, or targeted therapy for a solid tumor cancer; **3)** able to perform basic activities of daily living; **4)** cognitively oriented to time, place, and person (*determined by recruiter*); **5)** reporting severity of >2 on depression or >4 on anxiety using a 0-10 standardized scale; **6)** able to speak and understand English or Spanish; **7)** access to a telephone and **8)** has a caregiver who can be in any relationship role (e.g., spouse, sibling, parent, friend) who can participate with them.

Exclusion criteria are: **1)** diagnosis of a psychotic disorder in the health record; **2)** nursing home resident; **3)** bedridden; **4)** currently receiving counseling and/or psychotherapy. Inclusion criteria for the caregivers are: **1)**

age 18 or older; **2)** able to speak and understand English or Spanish; **3)** access to a telephone; **4)** not currently receiving counseling and/or psychotherapy; and **5)** not currently treated for cancer.

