Response will be assessed using the depression and anxiety items of the GSDS administered during weekly calls to survivors. Based on the inclusion criteria and established and validated symptom cut points,²²⁴ survivors will enter with moderate or severe depression and/or anxiety (one symptom or both). The cut-points are anchored in how much symptoms are distressing the participant by interfering with enjoyment of life, social relationships, and general daily activities. Participants indicate the severity/distress from 1 to 10. For depression, the mild category corresponds to a severity score of 1, the moderate category corresponds to scores 2-3, and scores of 4-10 fall into the severe category. For anxiety, the mild category is

severity of 1-3, the moderate category corresponds to scores 4-5, and the severe category is 6-10. Survivors who start at severe or moderate on depression and/or anxiety symptoms at intake and end at a lower category by the week 4 observation will be called **responders to the intervention**.²²⁸ If a symptom was mild at intake, symptom response would not be applicable. Because responders demonstrate substantial improvement anchored to symptom distress after 4 weeks, responders will continue with the SMSH only intervention for another 8 weeks. **Non-responders to the intervention** are survivors who do not respond on either or both symptoms.^{224,251,252} Non-responding survivors and their caregivers will be re-randomized to either continue with the SMSH alone for 8 weeks to give it additional time or add TIP-C for 8 weeks to rigorously test the value added by the more intensive intervention in Aim 2. Total intervention time is 12 weeks.

Caregivers' and survivors' depression and anxiety. PROMIS-short forms 8: depression and anxiety²⁵³⁻²⁵⁶ will be administered at baseline, 13 and 17 week telephone interviews to provide greater detail and precision in the measurement of these outcomes, as compared to single GSDS items administered in weekly calls. We chose 8-item short forms to minimize respondent burden while maintaining measurement precision.

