Interventionists - All sessions are digitally recorded and about 10% randomly reviewed throughout the study to maintain quality, with written and verbal feedback given to the counselors. [name] will supervise the intervention quality control activities. Through weekly case supervision, we will maintain fidelity of the intervention and counselor adherence to protocols. We will evaluate adherence (number required elements discussed/ total number of elements). [name] will listen to all sessions in English from the first 5 dyads (40 hours of supervision) and then randomly review 10% of sessions throughout the study. A bilingual counselor will review sessions in Spanish using established protocols as in past studies. Counselors who do not maintain 90% adherence will not be given new cases until retraining has occurred, and [name] will assume responsibility for those existing cases. Following retraining, 5 dyads will be monitored to ensure that >90% adherence is achieved and then we will return to randomly selected monitoring for quality control. Anyone unable to adhere to the standardized protocols is replaced after a second retraining.

Data - Quality assurance reports will be prepared on a quarterly basis by the statistical research assistant supervised by [name] and reviewed by the study Coordinator and investigative team. That is, for the internal audit, someone independent of the data collector will check the data. Data from 10% of the recorded interviews and intervention sessions compared to database entries. The acceptable error rate is 0.3 %, i.e., 3 out of 1,000 fields. All errors are corrected during the QA check. [name] will oversee preparation of the data report distributed to all investigators at least 5 days before the scheduled meeting. The report will include the summary of cumulative and quarterly accrual, randomization, cumulative attrition, and attrition by study group, gender, and race/ethnicity, adverse events and serious adverse events, data completeness and quality, and study Consolidated Standards of Reporting Trials (CONSORT) chart. Reports will also inform the Investigators about missing, invalid, or inconsistent data on selected key variables. For the external oversight, [name] who is not involved in the study has agreed to participate in QA meetings.

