6. Identification of Adverse Effects- The following will be considered serious adverse events (SAE): death, attempted suicide, major depression, breach of confidentiality. Death, attempted suicide and major depression would not occur as a direct result of study interventions, however, could be encountered during implementation of this study due to the inclusion criteria of cancer survivors. A breach in confidentiality may result from participation in this study. The investigators have successfully trained staff to monitor and protect confidentiality of participants in large research studies conducted over the past two decades. Similar training strategies will be incorporated for training of staff in this study. Additionally, all research staff will complete the human subjects and HIPAA certification training.

The following will be considered adverse events (AE): severe symptoms requiring hospitalization or urgent care. Again, severe symptoms are not expected to result from participation in this study but may result from cancer, its treatment or other existing comorbid conditions.

Averse events and serious adverse events may be identified during implementation of the experimental protocols and are monitored by the Investigators in several ways.

Interviewers: Interviewers may identify both serious adverse events and/or adverse events

during completion of telephone interviews or telephone calls to schedule telephone interviews. **Interventionists:** The interventionists may identify both serious adverse events and/or adverse events during their telephone contacts with the participants.

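### Major depression counts as a serious adverse event, with no rule separating cases present at entry from new or worsened ones

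*Combined protocol and SAP*

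**What the plan says.** Section 10.0, item 6 (Identification of Adverse Effects), sets the SAE list: "The following will be considered serious adverse events (SAE): death, attempted suicide, major depression, breach of confidentiality". The same paragraph holds that death, attempted suicide and major depression would not result directly from the interventions, but "could be encountered during implementation of this study due to the inclusion criteria of cancer survivors". The text available names two routes by which events come to notice, interviewers and interventionists, each during telephone contact.

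Section 10.0, item 5 (Data), puts the events into the quarterly report, which covers "adverse events and serious adverse events, data completeness and quality" among other items.

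Section 3.0 admits survivors "reporting severity of >2 on depression or >4 on anxiety using a 0-10 standardized scale", with no upper limit. Its mental-health exclusions are "diagnosis of a psychotic disorder in the health record" and current counselling or psychotherapy. Major depression is not among them.

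Section 6.0 says that "survivors will enter with moderate or severe depression and/or anxiety (one symptom or both"), and for depression on the General Symptom Distress Scale (GSDS) that "scores of 4-10 fall into the severe category".

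Section 1.0 gives a background rate: "Major depression occurs in approximately 16%, and subthreshold depressive disorders occur in 22% of cancer survivors during treatment".

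Section 8.0 (Potential Difficulties/Limitations) accepts that work on depression and anxiety could unintentionally do psychological harm, with referral as the response.

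**The concern.** A safety count is useful when a rise in it points to something that happened on study. Here one listed event is a condition that some survivors may already have when they enrol, and no counting rule deals with that. A counsellor who learns in week 2 of long-standing major depression and a counsellor who sees a survivor deteriorate in week 7 could both file the same SAE. Two staff members could also treat the same existing case differently, because the term is undefined.

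This blurs the harm most relevant to a psychological intervention. Section 8.0 treats psychological harm as possible, while section 10.0 rules out the intervention as a direct cause of major depression in advance. Given both statements, the tally needs to be able to show worsening.

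Detection is a second issue. If cases surface in conversation, groups with more conversation may yield more cases. An excess under TIP-C could then reflect contact time and not harm.

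**Working it through.** The plan states no figure for major depression at entry or for expected SAEs, so there is none to reproduce. The check is a comparison of the text, with two small calculations for scale.

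**Text comparison**

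1. Does the SAE term require onset or worsening after baseline? Section 10.0, item 6: no such condition, and no instrument or definition.
2. Can a survivor with major depression enrol? Section 3.0: yes. There is a floor on symptom severity and no ceiling, and the diagnosis is not an exclusion. Those already in counselling or psychotherapy are kept out, but that concerns treatment and not diagnosis.
3. Is the overlap recognised? Section 10.0, item 6: yes, it is attributed to the inclusion criteria. No counting rule follows.
4. Is a diagnostic assessment described at baseline or later? No. Section 6.0 gives the GSDS items and the 8-item PROMIS depression form, both symptom measures.

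So nothing in the stated rule keeps a case present at entry out of the tally.

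**Possible number of survivors affected (illustration)**

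Inputs: 298 survivors (section 4.0); 16% major and 22% subthreshold depression among survivors in treatment, and about 30% with psychological distress (section 1.0). Formula: number = 298 × assumed share.

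- Unselected rate: 298 × 0.16 = 47.7, about 48.
- If every entrant had major or subthreshold depression: 16/(16 + 22) = 0.421, and 298 × 0.421 = about 125.
- If all major depression lay within the 30% with distress and entrants were drawn from that group: 16/30 = 0.533, and 298 × 0.533 = about 159.

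The last two rest on strong assumptions. Entry on anxiety alone and the counselling exclusion push the share down, possibly below 16%; selection on distress pushes it up. These are possible existing cases, not predicted SAE reports. Caregivers, who have no depression criterion, are not counted.

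**Contact time**

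Section 7.0: a TIP-C+SMSH call lasts 40 minutes, of which the first 10 follow the SMSH procedure; an SMSH call lasts about 10. The extra time is 8 sessions × 30 minutes = 240 minutes, or 4 hours, per participant.

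- Second randomisation (TIP-C added against SMSH continued): the difference is the full 240 minutes.
- First randomisation: by the planned numbers in section 4.0, 60 of the 172 dyads starting on SMSH alone later receive TIP-C. Their arm averages 240 × 60/172 = 84 extra minutes per participant, so the difference between arms is about 240 − 84 = 156 minutes.

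**The case against.** The strongest reply is that the plan saw the overlap and chose broad reporting, and that depression is measured thoroughly elsewhere. Much of this stands.

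- A reader might infer that survivors in the severe GSDS band already have the SAE condition. The documents do not support that. The band is a cut on one self-rated item, section 1.0 treats major depression as a clinical category, and entry on anxiety alone is allowed.
- A reader might infer that the protocol orders existing cases to be reported. It does not say so. Item 6 speaks of events identified while the protocol is being carried out, which could be read as on-study occurrences. The defect is that the text does not settle which reading applies.
- A reader might infer that worsening would go unseen in the trial. It would not. The GSDS depression item is taken at baseline, weekly and at weeks 13 and 17, PROMIS depression at baseline and weeks 13 and 17, and the models in section 8.0 adjust for the baseline outcome. Worsening at group level would show there. What cannot show it is the SAE tally, and the text available does not link the outcome data to safety review.
- A reader might infer that TIP-C will produce more SAE reports. That is plausible but not shown. All groups have the same GSDS procedure at each call, and the report's split by study group is clearly attached to attrition, not clearly to SAEs.
- The text on how events are identified may be incomplete, so nothing is concluded from the absence of other routes or of reporting timelines.

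None of this supplies a rule for status at entry.

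**Conclusion.** The point holds in this form: major depression is an SAE with no distinction between cases present at entry and cases that are new or worse, in a trial that selects for elevated depression or anxiety and does not exclude the diagnosis. The SAE tally cannot separate the two, and longer TIP-C contact may add unequal detection.

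The size is uncertain. About 48 of 298 is what the plan's unselected 16% would give; it is neither a lower bound nor an estimate for this sample. How many cases would be recorded is unknown, because no diagnostic assessment is described.

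No efficacy analysis depends on this count, and no stopping rule tied to it appears in the text available. It should be corrected so that the safety report can be interpreted; it does not threaten the trial's main comparisons.

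**What to change.** Reconcile section 3.0, section 6.0, the limitations text in section 8.0 and section 10.0, item 6. In the safety plan:

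1. Keep recording every case of major depression found. Limiting the SAE to new or worsened cases could lose unrecognised cases first found on study.
2. Mark each case as present at entry or as new or worsened since baseline, using the baseline PROMIS depression and GSDS scores and any diagnosis seen in the health record. Allow for cases that this information cannot classify.
3. Report the categories separately in the quarterly report.
4. Add one table, by randomised group for each randomisation, of individual worsening from baseline on PROMIS depression at weeks 13 and 17, for survivors and caregivers. State in advance how worsening is summarised.

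The table draws on interviews given to both dyad members whatever their group, so it does not depend on what surfaces in counselling calls. PROMIS is a symptom score and does not establish a diagnosis; the table supplements the SAE list and does not define major depression. The health-record items listed in section 6.0 do not include psychiatric diagnoses, so that source will help only where one happens to be seen.

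The cost is one flag per case and one table, with no new assessment. No entry threshold or clinical rule is proposed.

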Randomization. Following the baseline interview, dyads will be randomized to either SMSH alone (N=172 post-attrition) or to TIP-C+SMSH (N=60 post-attrition). A minimization algorithm will be programmed by [name] to balance arms by recruitment location, site of cancer, stage of cancer (early versus late), type of treatment, and survivor's relationship to the caregiver (spouse vs non-spouse).²³⁹ The second randomization will occur for those who do not respond to the SMSH alone after the first 4 weeks using the same approach as the first randomization except in 1:1 ratio. The study coordinator will run the computer algorithm from the main study office (Tucson) to ensure allocation, concealment, and blinding.

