Potential problems from recruitment and retention will be minimized by the use our previous methods yielding high retention rates with no differential attrition between conditions. Potential problems in intervention delivery will be minimized by implementing protocols to maintain intervention fidelity. There are no high-risk aspects of this trial, and all procedures are non-invasive. We recognize that in addressing depression and anxiety our efforts might inadvertently produce detrimental psychological responses. Should this occur, our experienced interventionists will refer the survivor and/or caregiver to mental health services. Because randomizations may not account for all possible error sources, we will adjust for baseline values of outcomes in the analysis to provide added control over possible confounding preintervention influences. Three primary outcomes (depression, anxiety, and summed severity of other symptoms) and all hypotheses are stated a priori. In the exploratory analyses, the Benjamini-Hochberg or Hochberg adjustment²⁷⁷⁻²⁷⁹ will be used to control the false discovery rate.

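### The safety plan presumes that suicide attempts and major depression are not caused by the interventions, against its own limitations text, and specifies no adverse event reporting by study group

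*Combined protocol and SAP*

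**What the plan says.** Section 10.0, item 6 (Identification of Adverse Effects) lists as "serious adverse events (SAE): death, attempted suicide, major depression, breach of confidentiality". It then states that "Death, attempted suicide and major depression would not occur as a direct result of study interventions", and explains that such events might still be met because the trial enrols cancer survivors. The next paragraph defines adverse events as symptoms bad enough to need admission or urgent care, and says that "severe symptoms are not expected to result from participation in this study".

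Section 8.0 (Potential Difficulties/Limitations) takes a different line: "We recognize that in addressing depression and anxiety our efforts might inadvertently produce detrimental psychological responses". If that happens, "our experienced interventionists will refer the survivor and/or caregiver to mental health services".

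Section 10.0, item 5 (Data) sets out the quarterly report. Among its contents are "attrition by study group, gender, and race/ethnicity, adverse events and serious adverse events, data completeness and quality". External oversight is one person "who is not involved in the study has agreed to participate in QA meetings".

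Section 4.0 gives the first allocation as "SMSH alone (N=172 post-attrition) or to TIP-C+SMSH (N=60 post-attrition"). Non-responders to SMSH alone are then re-randomised 1:1.

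**The concern.** Whoever classifies a serious event has two statements to work from. One settles causality for three of the four listed event types before any has occurred. The other accepts that the intervention can do psychological harm. If the first is followed as written, a suicide attempt during counselling is recorded as unrelated by default.

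The usual safeguard against a wrong individual judgement is a comparison of event counts between randomised groups. Here that comparison is not specified. It matters more than usual because background events are expected: section 1.0 puts major depression at about 16% of survivors during treatment, and section 3.0 selects survivors with raised depression or anxiety. Against that background, a count without a concurrent comparison says little about the intervention.

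**Working it through.** No sample size, power or alpha figure is at issue, so there is no plan figure to reproduce. The check is mainly of the text, followed by two short calculations.

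**1. The two statements on causality.** Section 10.0 excludes a direct causal role for death, attempted suicide and major depression. Section 8.0 accepts possible psychological detriment without naming an event. They differ in wording (direct result; unspecified responses), but major depression is plainly a detrimental psychological response. One assessor cannot apply both to the same case. The section 8.0 sentence on handling gives referral and mentions no recording or relatedness step.

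**2. Does the explanation cover everyone?** Section 2.0 enrols 298 survivors and 298 caregivers, so caregivers are 298/596 = 50% of participants. Section 7.0 gives caregivers the same TIP-C protocol. Section 3.0 admits only caregivers not currently treated for cancer. An explanation based on enrolling cancer survivors therefore does not reach half the participants, while section 8.0 names caregivers among those who might be harmed.

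**3. The report contents.** On the plain reading of the list, study group, gender and race/ethnicity qualify attrition. Adverse and serious adverse events follow as a separate item with no qualifier. No available text plans a by-group table or analysis of the serious event list, quarterly or final.

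**4. What is compared by group anyway.** Section 2.0 makes depression, anxiety and summed severity of other symptoms primary, and hospital, urgent care and emergency department use secondary. Section 8.0 tests the group effect for each. The service-use outcomes overlap with the adverse event definition. Attempted suicide, death and a diagnosis of major depression are in none of these models, and mean symptom scores would not reveal a few suicide attempts.

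**5. What an undivided list can hide (assumed counts).** The documents give no expected number of serious events, so a range is shown.
- Share of dyads in TIP-C+SMSH after the first randomisation: s = 60/232 = 0.2586.
- Chance of r or more of k events falling there with no true difference: sum over j = r to k of C(k,j) s^j (1−s)^(k−j).
- For k = 5, r = 4: 5 × 0.2586^4 × 0.7414 + 0.2586^5 = 0.0166 + 0.0012 = 0.018.

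| Total events k | Marked imbalance | Probability | Milder imbalance | Probability |
|---|---|---|---|---|
| 3 | 3 | 0.017 | 2 or more | 0.166 |
| 5 | 4 or more | 0.018 | 3 or more | 0.113 |
| 8 | 6 or more | 0.005 | 4 or more | 0.126 |
| 10 | 6 or more | 0.023 | 5 or more | 0.089 |

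This assumes independent events, equal follow-up per dyad and equal detection. A list without group shows only k. A by-group list would show the marked imbalances, while the milder ones would remain compatible with chance.

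The first-stage contrast is also diluted. Of the 172 SMSH-first dyads, 120 are expected to be non-responders and 60 of those add TIP-C, which is 60/172 = 35%. Both randomisations therefore need to be shown.

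**6. Detection.** Section 7.0 gives about 10 minutes for an SMSH call and 40 minutes for a TIP-C call, for 8 of the 12 weeks. Scheduled call time per participant is 8 × 40 + 4 × 10 = 360 minutes with TIP-C and 12 × 10 = 120 minutes without, a ratio of 3. The first 10 minutes are common to all groups (weekly GSDS), but the counselling time gives more opportunity to hear of an event. By-group counts need the source of detection beside them.

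**The case against.** The strongest reply is that the plan already compares the relevant harms by group. Depression and anxiety are measured weekly, PROMIS forms are given at baseline and weeks 13 and 17, and service use is analysed by type. This stands. A reader might infer that a harm confined to one group could not be seen at all, and the documents do not support that: worsening mood and extra admissions would show in the Aim 1 and Aim 2 analyses. What those analyses leave out is the rare serious events, and any by-group view of safety while the trial is running.

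A reader might also infer that the external overseer receives a single pooled number. The plan does not say so. The format is unspecified, and nothing states that events are pooled or blinded.

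The conflict can also be read more mildly. Section 10.0 says direct result, and the following paragraph speaks of what is expected, so the sentence may be an expectation and not a rule of attribution. The listed events are serious adverse events whatever their cause and belong in the report. This softens the point, but the sentence still reads as a conclusion on causality, and no other relatedness standard appears in the available text.

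Finally, the list of monitoring routes in item 6 names interviewers and interventionists and then stops, and sections 11 and 12 are not in the available text. A relatedness procedure may lie there. That limits the claim of absence, but it does not resolve the conflict between sections 8.0 and 10.0.

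**Conclusion.** The point holds in a limited form. Section 10.0 presumes non-relatedness for death, attempted suicide and major depression; section 8.0 contradicts it in substance; and the stated reason does not apply to caregivers. By-group reporting of adverse and serious adverse events is not specified, so an imbalance in rare serious events could go unnoticed in the quarterly reports.

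The documents allow no estimate of how likely such an imbalance is. The table above shows only what an undivided list would conceal under assumed counts. The conclusion rests on the plain reading of the report list and, for the missing relatedness procedure, on the available text being complete. It does not imply that the interventions are harmful, and it does not affect the efficacy analyses. The change should be made because participants are selected for distress and the correction is cheap.

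**What to change.** 1. Reconcile section 8.0 (Potential Difficulties/Limitations) with section 10.0, item 6. Remove the advance statement of non-relatedness and state that relatedness is assessed event by event, for survivors and for caregivers. If a procedure already exists elsewhere in the full protocol, cross-refer to it and align the wording.
2. In the existing quarterly report, tabulate adverse and serious adverse events by randomised group for the external overseer, separately for the first and second randomisation and for survivors and caregivers, with person-weeks as the denominator.
3. Mark how each event was detected: common weekly assessment, week 13 or 17 interview, or counselor session. As described, the common assessments cover symptoms and service use and include no question on suicide attempts, so the table should say which event types they can detect.

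The cost is a few sentences and one extra table in a report already produced each quarter. The one drawback concerns blinding: section 8.0 says data collectors are blinded, so the by-group safety table should be kept from them. Sample size, interventions and planned efficacy models are unchanged.
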